6.0 DATA MANAGEMENT CONSIDERATIONS

6.1 Data Management

The PI and participating site investigators will maintain adequate and accurate participant case histories with observations and other data pertinent to the study. Original source documents will be transcribed to data collection tools and used to communicate study data to the lead site.

Participating site PI ([name]/[name]) will be responsible for maintaining the clinical protocol and subjects' study charts, reporting adverse events, and reporting the status of the trial in continuing renewals submitted to their IRB and trial monitoring group(s) as per their facility protocol.

6.2 Confidentiality

Members of the local team will be responsible for database records of patient data. The data will be kept in the secure central online database (CarMa), under password protection, encrypted, and with access limited to specific areas of the database. A chart with all the relevant research patient information will be maintained for each patient at each institution by the local team for that specific institution. Study PI, statistician and research team abstracting information as well as data collectors for claims data and primary oncology team members will remain blinded to the randomization assignment. Study Coordinator at each site may review patient charts for yearly audits.

6.3 Protocol Review and Amendments

The protocol will be reviewed and approved by the Stanford IRB. The Protocol Director will disseminate any protocol amendment information to all participating investigators.

Statistical Analysis Plan (SAP)

Title: Lay Health Workers Engage, Educate, and Encourage Patients to Share (LEAPS)

1.1. Study Aims

1.1.1. Aim 1

The primary aim of the LEAPS program is to evaluate whether trained lay health workers who engage newly diagnosed patients with cancer and patients with newly diagnosed relapsed or progressive disease can improve Health-Related Quality of Life (HrQOL) at 4 months post-enrollment compared to baseline more than usual care.

1.1.2. Aim 2

Secondary aims which a priori defined to be exploratory include the effect of the intervention on changes in health-related quality of life from baseline to 12-months post-enrollment as compared to usual care, changes in patient satisfaction with decision-making and patient activation at 4- and 12-months post-enrollment as compared to baseline, change in emergency department and hospital use within 4- and 12-months post-enrollment, advance directive, goals of care documentation, and Physician Orders for Life Sustaining Treatment documentation at 4- and 12-months post-enrollment, and hospice and palliative care use within 4- and 12-months post-enrollment and total costs of care from baseline to death or 12-months follow-up, whichever is first. In addition, we will evaluate emergency department, hospitalization, hospice and palliative care use and total costs of care in the last 30 days of life among those who died.

2.4. Randomization

1:1 Randomization of participants using simple randomization strategy by site; allocation to either the 12-month intervention combined with usual oncology care or usual oncology care alone in Atlantic City, NJ and Chicago, IL.

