2.0 BACKGROUND AND RATIONALE

Many patients and families served by Unite Here Health express significant challenges with their cancer care. Many describe significant complications from social determinants of health, poor quality of life with difficult decisions, little understanding of the disease context, uncontrolled symptoms, and treatment and clinic visits that are provided at distances far from their residences. Oncology care delivery for vulnerable patients is often fragmented with poor care coordination, patient-provider communication challenges, and centralization of healthcare services that make care delivery and access even more difficult for vulnerable patients. These barriers in the delivery of care can result in disparate cancer outcomes.

The LEAPS intervention extends the spectrum of care up to 12 months post-enrollment (for patients with newly diagnosed, relapsed or progressive disease). The key elements of the intervention address three major challenges faced by vulnerable patient populations: 1) patients and their families who face social and economic challenges experience challenges in communication with their providers regarding their goals of care and understanding their prognosis; 2) patients experience difficulty in expressing their symptoms to their providers; and 3) patients experience challenges attending their clinic and treatment appointments due to financial burden, travel difficulties and/or lack of social support to drive and accompany them to their visits. (See Appendix for Rationale)

The proposed intervention addresses these three critical care elements by training and deploying culturally-sensitive, community-based health care workers who assist patients and families in identifying complications from social determinants of health such as transportation, financial or housing, discussing goals of care and advance care planning, proactively assess cancer-related symptoms with oversight from a UHH nurse, and assist in coordinating care delivery at home through leveraging telephonic discussions and home visits.

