If a patient is interested and consents verbally, he/she will be provided a welcome letter with basic information and contact phone numbers for the project. The patients will be randomized by Stanford biostatistician using a computer-generated ordered list of randomized numbers in each city. For all patients assigned to the LEAPS intervention arm, the community health worker will contact the patient to begin the intervention procedures that include assisting patients with understanding their goals of care, documenting goals of care, proactively assessing symptoms, and coordinating home-based or community-based care delivery. The intervention will be provided in addition to the usual care processes (Intervention details are provided in Appendix B).

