4.0 MATERIALS AND METHODS

After a patient is enrolled in the study, the patient will be registered and entered into the project database (CarMa) and assigned an identification number. The identification number will be used on all subject-specific documents and research-related forms.

During registration, patients will be randomized to two arms (Arm A: Usual Care or Arm B: LEAPS Intervention). Specifically, the patients will be randomized 1:1 using a simple randomization strategy in each site into two arms at each site.

All patients, throughout the study, will be asked to complete three surveys: 1) patient health-related quality of life (using Functional Assessment of Cancer Therapy – General (FACT-G) and 2) satisfaction with decision-making (Satisfaction with Decision Scale) and 3) the patient activation measure (Patient Activation Measure-13). A trained study staff member will administer the surveys at baseline (month 0) and again at 4 months and 12 months for patients in the intervention and usual care arm. Participant information will be entered into the CarMa database within 7 calendar days. Study team members will conduct electronic health record chart review of each participant and abstract date of the following: goals of care documented by oncology clinician, advance directive, and Physician Order for Life Sustaining Treatment. All health care claims data will be provided by UHH to the study team for each participant in the study at the study end which will consist of all charges and paid claims for total costs including outpatient, inpatient and pharmacy services. All study team members will be blinded to the randomization assignment. Only the community health workers will know the study assignment and the local site coordinator at each site.

As part of usual care, study PI and team members redesigned benefits such that any member of UHH with cancer will also receive waived copays if they choose to seek care at the preferred

provider in Atlantic City. We will also provide each member with access to transportation and other services to receive care at the preferred provider.

- Arm A: Usual Care (Control) / No Intervention

Patients in this arm receive “usual” care coordination from their care coordination team which includes case management by a registered nurse practitioner to address financial concerns, care navigation and coordination.

- Arm B: LEAPS/ Intervention Group

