The intervention will be comprised of a CHW assignment with a baseline introduction (either telephonic or in-person) of the program followed by a visit (telephonic or in-person) with the community health worker to screen for health-related social needs, identify and refer to community resources for any identified complication from social determinants of health and to begin intervention regarding goals of care and symptom management. All CHWs have undergone standardized training with additional supervised visits to gain skills in engaging patients and families in goals discussion and in symptom assessment algorithms (see Appendix for Details).

The CHW will contact patients based on patients’ ongoing needs but will provide at a minimum weekly support from time to enrollment up to 4 months post-enrollment and then monthly from 4-months post-enrollment until 12-months post-enrollment. The CHW will also conduct meetings with patient’s family and caregivers at the same time intervals where possible. The intervention details are provided in the Appendix.

Lay Health Worker Training

The PI and UHH staff provide ongoing training for the CHWs through formal classroom training (See Appendix for a list of topics covered), biweekly case rounds, shadowing and role plays. All CHWs will also be provided with previously tested and developed standardized training manuals that are refined based on feedback from stakeholders at UHH. The manuals include a highly detailed workflow of the project, from enrollment to completion. CHWs also will receive training on what to say during patient contact, advanced care planning conversations, documentation of advance care planning, the study calendar, data management, and key contact information. CHWs will also receive training on symptom management.

Supervision of the Lay Health Worker

The community health worker will be supervised by the RN at the Unite Here Health Fund offices in Chicago and Atlantic City. The RN will ensure that the protocol is carried out correctly and address any issues that may arise in the LHWs’ workflow. The CHWs at each site (2 0.4 FTE in Chicago, 3 0.3 FTE in Atlantic City) will participate in monthly meetings with the rest of the project members (at both Stanford and UHH) to review study accrual and program goals. At

these meetings, the RN will be responsible for providing a report on project progress and project issues incorporating feedback from the LHWs.

Quality of Life Measures

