4.2.1. Statistical Modeling

To assess our primary outcome of the effect of the intervention on change in health-related quality of life from baseline to 4-months post-enrollment between groups, we will calculate expected mean differences between groups by Generalized Estimating Equations (GEE) models where the outcome will be modeled as a function of treatment group, categorical time (baseline, 4 months, 12 months) and an interaction term between treatment group and time with an exchangeable correlation clustered within person. Significance will be assessed between groups overtime using a type III F-test on the interaction term. All ratios will be expressed as referent to the control group.

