4.2.2.1. Site-specific Modeling

We will consider refitting primary models for each site separately to explore the effect of site heterogeneity on our results.

Sample Size Considerations

The sample size of 160 participants (80 randomized to the intervention group and 80 randomized to the control group) provides greater than 90% power to detect difference in quality of life between groups (delta change =4) assuming a within-subject correlation of 0.8 and a standard deviation of the change in score equal to 9.5 based on our pilot data. The primary outcome was determined by our community partners.

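### Patients are randomised within city, but the primary GEE as shown has no site-by-time term; adding it is a small, low-cost gain in precision, not the repair of an invalid analysis

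*Combined protocol and SAP*

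**What the plan says.** **Allocation.** SAP 2.4 gives "1:1 Randomization of participants using simple randomization strategy by site". Protocol 3.1 has the biostatistician randomise "using a computer-generated ordered list of randomized numbers in each city", and protocol 4.0 says that "the patients will be randomized 1:1 using a simple randomization strategy in each site into two arms at each site". No blocks are mentioned.

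**Primary model.** In SAP 4.2.1 "the outcome will be modeled as a function of treatment group, categorical time (baseline, 4 months, 12 months) and an interaction term" between group and time, with an exchangeable correlation within person. The test is a type III F-test on that interaction. No site or site-by-time term is listed.

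**Site.** The one site analysis shown is in SAP 4.2.2.1: "We will consider refitting primary models for each site separately to explore the effect of site heterogeneity on our results". It names no between-city contrast.

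**Possible differences between the cities.** Protocol 4.0 lists separate staff: "The CHWs at each site (2 0.4 FTE in Chicago, 3 0.3 FTE in Atlantic City". Under usual care it also says that "any member of UHH with cancer will also receive waived copays if they choose to seek care at the preferred" provider in Atlantic City, with access to transport. Protocol 2.0 names as intervention targets "complications from social determinants of health such as transportation, financial or housing".

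**The concern.** City is part of the allocation scheme and is known for every patient before randomisation. If mean 4-month change in FACT-G differs between Atlantic City and Chicago, that difference sits in the residual variance of the planned model. Any chance imbalance in city mix between the arms then also carries into the treatment estimate. Simple randomisation does not prevent such imbalance. Including site in a form that acts on change removes both effects at almost no cost.

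The lesser matter is reporting. If the optional city refits are run and shown without a direct contrast, readers are left to compare two city p-values, or to take the absence of a significant difference as evidence of equal effects.

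At stake is a little precision and clearer reporting. The validity of the primary test is not in question.

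**Working it through.** **Inputs from the documents.** 160 patients, 80 per arm; difference in change of 4; SD of change 9.5; within-subject correlation 0.8; 5% significance level (protocol 5.1, SAP sample size section).

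**Assumed.** Two-sided test, complete data, true effect 4. City split 50/50 or 70/30. City gap D in mean change of 0, 2 or 4 points, the same in both arms.

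**1. The plan's own power figure (greater than 90%).** SE = SD × sqrt(2/80); power = Φ(4/SE − 1.96).
- SD of change 9.5, as worded: SE = 1.502, power = 75.9%.
- If 9.5 is the SD of a single score: SD of change = 9.5 × sqrt(2 × (1 − 0.8)) = 6.01, SE = 0.950, power = 98.8%.

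Only the second reading agrees with the stated figure. That is a separate and larger question, which a site term does not resolve. Both readings are carried below.

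**2. Which site term matters.** A site main effect is the same at every visit, so subtracting baseline removes it from the change contrast. This was checked in a three-visit exchangeable GEE, 150 datasets per scenario. With complete data, adding site alone moved the 4-month contrast by less than 1e-13. With 15% and 30% of values missing at random at 4 and 12 months, it moved by at most 0.08 points. At D = 4 with complete data, the mean robust SE was 1.517 with no site term, 1.517 with site only and 1.486 with site-by-time.

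**3. Gain at 4 months, 9.5 (or 6.01) taken as the within-city SD.** 60,000 simulated trials per cell, t-test on 4-month change without and with site, 50/50 split:

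| D | SE, SD 9.5 | Power, SD 9.5 | Power, SD 6.01 |
|---|---|---|---|
| 0 | 1.505 / 1.509 | 75.2 / 75.0% | 98.7 / 98.6% |
| 2 | 1.512 / 1.509 | 74.6 / 74.8% | 98.5 / 98.6% |
| 4 | 1.538 / 1.509 | 73.1 / 74.8% | 97.7 / 98.7% |

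Across the splits tried, the change at SD 9.5 is -0.2 to -0.35 points at D = 0, +0.1 to +0.2 at D = 2 and +1.2 to +1.7 at D = 4. At SD 6.01 it is about -0.1, +0.1 and +0.8 to +0.9 points.

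**4. The same, with 9.5 as the total SD.** Residual SD = sqrt(9.5² − p(1 − p)D²), where p is one city's share. For p = 0.5 and D = 4: sqrt(90.25 − 4) = 9.29, SE = 1.468, power = 77.8% against 75.9%, a gain of 1.9 points. At 70/30 the gain is 77.5 − 75.9 = 1.6 points. This approximation ignores the small cost of estimating site, so it shows no loss at D = 0.

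**5. The 2-df test in SAP 4.2.1.** Noncentral F, SD 9.5, 50/50 split, changes at 4 and 12 months correlated 0.5, same gap at both visits; power without / with site:
- 12-month effect 4: 78.4/78.1%, 77.8/78.1%, 75.9/78.1% at D = 0, 2, 4.
- 12-month effect 2: 65.3/65.0%, 64.7/65.0%, 63.3/65.0%.
- 12-month effect 0: 78.4/78.1%, 78.2/78.1%, 77.8/78.1%.

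The pattern is the same: about 0.3 points lost at D = 0, and 0.3 to 2.2 gained at D = 4.

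**6. Validity and chance imbalance.** In a separate simulation (8,000 trials per setting, D = 4, 50/50), type I error without / with site was 5.4/5.8% at SD 9.5 and 5.9/6.0% at SD 6.01, so leaving site out does not raise it. The arms' city shares differ by more than 10 percentage points in about 24% of trials at 50/50 and 17% at 70/30. At D = 4, a 10-point imbalance shifts the unadjusted estimate by 0.10 × 4 = 0.4 points.

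**7. Between-city contrast in the treatment effect.** SE = SD × sqrt(4/n1 + 4/n2); half-width = 1.96 × SE.
- SD 9.5: SE 3.00 (80/80) or 3.28 (112/48); half-width 5.9 or 6.4 points.
- SD 6.01: SE 1.90 or 2.07; half-width 3.7 or 4.1 points.

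Against a target effect of 4, the contrast is imprecise on either reading.

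**The case against.** The strongest case against is that nothing here is broken. Simple allocation within each city forces no balance, so the usual reason for analysing by randomisation stratum (that ignoring forced balance misstates the variance) does not apply. This stands. A reader might infer from randomisation by city and a model without site that the primary test is biased or has the wrong error rate. The design as described does not support that.

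Nor is the gain assured. Interpolating the step 3 SEs in D² between 0 and 2, adjustment breaks even at D² ≈ 4 × 0.004/0.007 = 2.3, a gap of about 1.5 points; below that it loses a trace of precision. A visible gain needs a gap near 4, as large as the target effect itself. This stands too, but the loss is at most about 0.35 points.

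A reader might also infer that delivery, or the intervention's effect, is shown to differ by city. It is not. Protocol 4.0 describes separate teams, but with standardised training and manuals, nurse supervision and one minimum contact schedule. The copay and transport benefits belong to usual care and so reach both arms. These facts make a city difference plausible and no more.

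Site is not ignored either. SAP 4.2.2.1 is devoted to it, and the between-city difference can be had by subtracting two independent refits. Leaving so imprecise an exploratory analysis optional is defensible, and nothing in the documents says that city p-values will be compared.

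Finally, the SAP text available passes from 4.2.1 to 4.2.2.1 without a section 4.2.2, and section 4 mentions relevant covariates without listing them. An adjusted model in 4.2.2 cannot be ruled out; none is shown.

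**Conclusion.** The point holds as a free improvement. The primary model as shown does not use the site factor by which patients are allocated, and including site-by-time is the better choice at almost no cost.

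With 9.5 as the within-city SD of change, power for the 4-month contrast changes by about -0.3 points at a city gap of 0, +0.2 at 2 and +1.2 to +1.7 at 4. With 9.5 as the total SD, the gain at a gap of 4 is similar. If the SD of change is 6.01, the changes are smaller. All of this assumes complete data, a true effect of 4, and city splits and gaps that the documents do not give. Apart from power, adjustment protects the estimate from chance imbalance in city mix.

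The reporting of city results is a secondary wording point and would not justify a comment alone. The conclusion is also conditional on section 4.2.2 not already containing such a model.

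**What to change.** **SAP 4.2.1.** Add site and site-by-time to the primary GEE and keep the group-by-time interaction as the treatment comparison. State that site enters through its interaction with time because the outcome is change. If section 4.2.2 already specifies this adjustment, say there or in 4.2.1 which model is primary.

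**SAP 4.2.2.1 (secondary).** If city results are shown, report with them one exploratory treatment-by-site contrast in 4-month change, from a separate supportive model, with its 95% CI. Describe it as imprecise, say that a non-significant result does not show equal effects, and say that the two city p-values will not be compared. Note that city and community health worker team cannot be separated. Quote no power for this contrast until the SD behind the sample size is clarified.

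**Cost.** SAP wording, to be settled before data are analysed; 3 model degrees of freedom (one for site, two for site-by-time) with 160 patients; and about 0.3 points of power if site turns out to be irrelevant. Site is known from the allocation lists, so no new data are needed.

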3.3 Enrollment

The target number of subjects at the site is 160 (80 per arm). Patient enrollment will continue until sample size is reached (anticipated 24 months). Data collection will occur at baseline and months 4 and months 12 for each patient in the study. The data follow-up period (to assess utilization) will occur for up to 12 months following each patient enrollment or death (whichever is first).

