5.0 STATISTICAL CONSIDERATIONS

5.1 Outcome Measurements

None of the listed outcomes relate to safety.

Primary Outcome Measure

The specific key measurement used to measure the effect of the intervention corresponding to the primary outcome is change in health-related quality of life. The protocol aims primarily to detect a significant (5% significance level) between-group difference from baseline to 4 months (delta

change=4) assuming a within-subject correlation of 0.8 and a standard deviation of the change in score equal to 9.5 based on empirical evidence.

Secondary Outcome Measure

Patient satisfaction and activation will be explored using changes in the Patient Satisfaction with Decision Scale and Patient Activation Measure. Utilization will be measured evaluating comparisons of hospitalizations, emergency department, and referrals to hospice and palliative care. Advanced care planning will be measured by comparing rates of advance directive documentation, Physician Orders for Life-Sustaining Treatment, and goals of care documentation in patients' electronic health record charts. Patient survival will also be compared between groups. Total costs of care will be abstracted from UHH database only to conduct a budget impact analysis and obtain point estimates for refinement of the intervention in anticipation of a larger multi-center trial. A cost-effectiveness analysis is not planned and will not occur until effectiveness has been demonstrated in subsequent studies upon completion of this study.

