5.3 Sample Size

The primary goal is to improve quality of life. A total of 160 patients are needed to attain significant between-group differences from baseline to 4 months after study enrollment for patients. (See Primary Outcome Measure section above).

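### Simple randomisation from a separate list in each city gives no balance by city and does not guarantee 80 per arm, and the target of 160 is worded as a per-site number

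*Combined protocol and SAP*

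**What the plan says.** **Method.** Protocol 4.0 states that "the patients will be randomized 1:1 using a simple randomization strategy in each site into two arms at each site". SAP 2.4 agrees: "1:1 Randomization of participants using simple randomization strategy by site", for Atlantic City and Chicago. Protocol 3.1 (Consent Procedures) adds that a Stanford biostatistician works from a computer-generated list for each city. No section mentions blocks, another restriction or a cap on imbalance.

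**Numbers.** SAP Sample Size Considerations describes the 160 participants as "80 randomized to the intervention group and 80 randomized to the control group" and bases the power statement on that split. Protocol 5.3 says "A total of 160 patients are needed". Protocol 3.3 says "The target number of subjects at the site is 160 (80 per arm", and adds that enrolment goes on until the sample size is reached.

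**Model.** The primary GEE in SAP 4.2.1 contains treatment group, categorical time and their interaction. It has no term for city. SAP 4.2.2.1 says that separate fits by site will be considered, to explore heterogeneity.

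**The concern.** Keeping a separate list for each city is normally the first half of stratified randomisation. The second half is a restriction, such as blocking, that holds the arms close to equal within each list. Without it, separate lists have no effect on balance: each patient is still an independent 1:1 toss. The plan therefore has two lists without the benefit that usually motivates them, and it states as numbers randomised a split that the method does not secure.

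City could matter. The copay waiver in Protocol 4.0 is tied to the preferred provider in Atlantic City. Community health worker staffing also differs (two at 0.4 FTE in Chicago, three at 0.3 FTE in Atlantic City). If change in FACT-G differs between cities, a chance imbalance in city mix goes unadjusted in the primary model. The fits by city would rest on whatever split chance gives.

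The wording of the target is a separate matter. The sentence in Protocol 3.3 governs when accrual stops, and it disagrees with two other statements of the sample size.

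**Working it through.** **Inputs.** Total 160, as 80 and 80 (SAP Sample Size Considerations). Difference in change 4 ("delta change =4"), SD of change 9.5, within-subject correlation 0.8 (same section). "5% significance level" (Protocol 5.1); sidedness is not stated, so two-sided is assumed. The split of patients between cities is not given, so a range is shown.

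**1. The plan's own figure.** Power = Φ(δ / (σ·√(1/n₁ + 1/n₂)) − 1.96). At 80:80 the standard error is 9.5 × √(2/80) = 1.502, and 4/1.502 = 2.663, so power = Φ(0.703) = 75.9%. The stated figure of more than 90% does not reproduce on these inputs. It is exceeded if 9.5 is the SD of a single score: the SD of change is then 9.5 × √(2 × (1 − 0.8)) = 6.01 and power is 98.8%. That is a separate issue; both readings are carried below.

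**2. Arm sizes under simple randomisation.** One arm's size is Binomial(160, 0.5), with SD √(160 × 0.25) = 6.3.
- P(exactly 80:80) = 6.3%
- 95% range for one arm: 68 to 92
- P(90:70 or more uneven) = 13.3%

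**3. Do separate lists help?** The sum of independent Binomial(a, 0.5) and Binomial(160 − a, 0.5) is Binomial(160, 0.5). Convolving the two numerically for city splits 80/80, 100/60, 120/40 and 140/20 gave agreement with a single list to within 1e-16. Separate simple lists add no balance.

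**4. Power cost.**

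| Split | SD of change 9.5 | SD of change 6.01 |
|---|---|---|
| 80:80 | 75.9% | 98.8% |
| 70:90 | 75.2% | 98.7% |
| 68:92 | 74.9% | 98.6% |
| Average over all splits | 75.6% | 98.7% |

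On the literal inputs, an exact split gains 75.9 − 75.6 = 0.3 points on average and 75.9 − 74.9 = 1.0 point at the edge of the 95% range.

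**5. City balance (city sizes assumed).**

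| Patients per city | 95% range of one arm, larger city | Same, smaller city | P(city mix differs between arms by 10 points or more) |
|---|---|---|---|
| 80 / 80 | 31 to 49 | 31 to 49 | 23.6% |
| 100 / 60 | 40 to 60 | 22 to 38 | 19.9% |
| 120 / 40 | 49 to 71 | 14 to 26 | 15.7% |
| 140 / 20 | 58 to 82 | 6 to 14 | 6.0% |

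At 80/80, the SD of the difference in city share is √(2 × 0.25/80) = 0.079, so its 95% range is about ±15 points. As an illustration, suppose the cities differ in mean change by 4 points, the whole target effect (assumed). A 15-point imbalance then moves the estimate by 0.15 × 4 = 0.6 points, against a standard error of 1.5.

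**6. The target.** Protocol 5.3 gives 160 as a total, and the SAP gives 80 + 80 = 160. Protocol 3.3 read literally for two cities gives 2 × 160 = 320, or 160 per arm. Power would then be Φ(4 / (9.5 × √(2/160)) − 1.96) = 96.5%, against 75.9% at 160.

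**The case against.** The strongest case on the other side is that this is a design preference. Protocol and SAP agree on the method. Simple randomisation is sound at 160 patients, the test keeps its type I error, and 80 per arm is an ordinary planning figure under 1:1 allocation. All of that stands.

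The harm from city imbalance is also limited. The primary test concerns change over time, so a stable difference in level between cities largely cancels; only a difference in change matters, and no section shows one. The copay waiver is part of usual care and open to both arms. Chance imbalance is already within the sampling variability that the test allows for. The city figures depend on assumed splits, and the fits by city are exploratory and optional. These points stand too and keep the matter minor.

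Blocking also has a cost. Protocol 4.0 lets the community health workers and local site coordinators know assignments, so blocks bring some predictability that simple randomisation avoids. Blocking by city without a city term in the model would be half a remedy, since inference then tends to be conservative. Both points shape the fix.

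The list described in Protocol 3.1 could conceivably have a fixed total per arm. No section says so, and the word *simple*, used in both documents, points the other way.

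On the target, the reply is that *at the site* is a slip, since the same sentence gives 80 per arm. That is very probably right. It is still worth correcting in the sentence that tells staff when to stop enrolling.

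**Conclusion.** The point holds as a minor one. The randomisation is valid, but it gives no balance by city and makes 80 per arm an expectation, with a 95% range of 68 to 92. The arm-size result follows from the stated method and a total of 160. The power cost assumes the documents' difference of 4, a two-sided 5% test and complete data, and is about 1 point at most within that range under either reading of the SD. The city-mix probabilities, 6.0% to 23.6%, rest on assumed city sizes.

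A reader might infer three stronger things that the documents do not support:
- **That the comparison is biased or the allocation wrong.** The stated ratio is 1:1, and the method has it.
- **That unequal arms explain why power above 90% does not reproduce.** Power is 75.9% on the literal inputs even at exactly 80:80.
- **That 320 patients are intended.** Protocol 5.3 and the SAP both make 160 the total. Only the wording of Protocol 3.3 is at fault.

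**What to change.** **If allocation has not begun.** In SAP 2.4 and Protocol 4.0, specify 1:1 permuted blocks of randomly varying size (for example 4 and 6), generated separately for each city and allocated centrally, with block sizes not disclosed to the sites. An incomplete block of 6 leaves a difference of at most 3 in a city, so at most 6 overall, or 83:77. In SAP 4.2.1, add city and city-by-time terms to the primary GEE. Name a holder of the list other than the blinded analyst: Protocol 3.1 has a biostatistician randomise, while Protocol 6.2 and SAP 2.5 blind the statistician.

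**If allocation has begun.** Keep simple randomisation, add the same model terms before any unblinded analysis, and describe the arms in Protocol 3.3 and SAP Sample Size Considerations as *about 80 each (expected range 68 to 92)*.

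**In either case.** In Protocol 3.3, replace *at the site* with *in total across both cities*.

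**Cost.** A new pair of computer lists, two model terms and a few lines of text. The downside of blocking is slight predictability near the end of a block; varying sizes and central allocation keep it small.
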